10.2.3 SAFETY REVIEW

Evaluation is based on strict stopping criteria for unacceptable toxicities. Specifically, in the 1st stage, we continuously evaluate toxicity for the 1st 16 patients (e.g., patients in first stage of Phase II study). Toxicity will be also evaluated at end of the 2nd stage for the total 25 patients. We consider 20% as the maximum allowable unacceptable toxicity rate (failure to engraft included) with a 0.05 probability of stopping early. Sequential boundaries will be used to monitor dose-limiting toxicity rate as outlined by Ivanova et al. [59]. The accrual will be halted if excessive numbers of dose-limiting toxicities are seen, that is, if the number of dose-limiting toxicities is equal to or exceeds b_n out of n patients (see table below).

Number of Patients, n	1	2	3	4	5	6	7	8	9	10	11	12	13	14	15	16
Boundary, b_n	-	-	3	4	4	4	5	5	5	6	6	6	7	7	7	7

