6.1.9 DURATION OF THERAPY

The duration of ibrutinib therapy will be up to 51 weeks.

The duration of therapy of pembrolizumab will be up to 51 weeks. Pembrolizumab dosing could be extended for up to 2 years if clinical benefit per investigator.

Patients will be considered evaluable if they complete at least 9 weeks or three infusions of pembrolizumab.

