8.3 TIME PERIOD AND FREQUENCY FOR EVENT ASSESSMENT AND FOLLOW-UP

The occurrence of an AE or SAE may come to the attention of study personnel during study visits and interviews with study participants presenting for medical care, or upon review by a study monitor. All AEs, including local and systemic reactions not meeting the criteria for SAEs, will be captured on the appropriate CRF. Information to be collected includes event description, time of onset, clinician’s assessment of severity, relationship to study product (assessed only by those with the training and authority to make a diagnosis), and time of resolution/stabilization of event. All AEs occurring during the study must be documented appropriately, regardless of relationship. All AEs will be followed to adequate resolution.

Any medical condition that is present at the time that the participant is screened will be considered as baseline and not reported as an AE. However, if the study participant’s condition deteriorates at any time during the study, it will be recorded as an AE. UPs will be recorded in the data collection system throughout the study.

Changes in the severity of AEs will be documented to allow an assessment of the duration of the event at each level of severity to be performed. AEs characterized as “intermittent” require documentation of onset and duration of each episode in the medical record.

Adverse events for the purpose of this study will be reported from the time period beginning when the consent form is signed until 90 days after the end of pembrolizumab infusions and 30 days after the last dose of ibrutinib. At each study visit, the investigator will inquire about the occurrence of AE/SAEs since the last visit. Events will be followed for outcome information until resolution or stabilization are achieved. Any AE present at the time of final study closure will be considered ongoing.

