8.5 STUDY HALTING RULES

Safety assessments will consist of monitoring and recording all adverse events and serious adverse events, the regular monitoring of hematology and blood chemistry parameters and regular physical examinations. Adverse events will be evaluated continuously throughout the study. Safety and tolerability will be assessed according to the NIH/NCI Common Terminology Criteria for Adverse Events version 5.0 (CTCAE v5.0) that is available at: <http://evs.nci.nih.gov/ftp1/CTCAE/About.html> The Protocol Monitoring Committee (PMC) at Moffitt monitors its assigned ongoing research protocols for: adverse event reporting, data and safety monitoring, and internal audit findings. The PMC, upon review of any agenda item, may approve the study for continuation, require revisions, suspend or close a protocol.

Investigators of studies which are designated to be reviewed by the PMC for data and safety monitoring, shall provide a statistical report of the study's progress and summary of adverse events and deviations based on the phase of the study and the associated risk of the study or more often if applicable. The PI will be notified for recommendations or notifications after the PMC review in regards of continuation or stopping the clinical trial

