10.2 DESCRIPTION OF STATISTICAL METHODS

10.2.1 ANALYSIS OF THE PRIMARY EFFICACY ENDPOINT(S)

The Simon's minmax two-stage design will be used to test the null hypothesis that complete response (CR) \leq 10% versus the alternative that CR \geq 30% with 90% power and a type I error rate of 10%. This will result in an expected sample size of 20.37 and a probability of early termination of 0.52. After testing the drug combination on 16 patients in the first stage, the trial will be terminated if 1 or fewer respond. If the trial goes on to the second stage, a total of 25 patients will be studied. If the total number responding is less than or equal to 4, the drug combination will be rejected. Statistical analyses will be descriptive in nature. Patients' demographics, AEs and serious AEs, disease status, and CR will be summarized by descriptive statistics.

Clinical response rates will be calculated with 95% CIs.

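### The toxicity stopping boundary ends at patient 16; patients 17 to 25 have no numeric limit, and the one stage-2 look comes after accrual is complete

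*Combined protocol and SAP*

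**What the plan says.** Section 10.2.3 opens with "Evaluation is based on strict stopping criteria for unacceptable toxicities". It then specifies that "in the 1st stage, we continuously evaluate toxicity for the 1st 16 patients", and gives a table of limits b_n: none for n = 1 and 2, then 3, 4, 4, 4, 5, 5, 5, 6, 6, 6, 7, 7, 7, 7 for n = 3 to 16. The table ends there. The maximum allowable toxicity rate is 20%, with a 0.05 probability of stopping early. The action on reaching b_n is "The accrual will be halted if excessive numbers of dose-limiting toxicities are seen". For stage 2 the section offers only "Toxicity will be also evaluated at end of the 2nd stage for the total 25 patients".

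Section 10.2.1 sets the efficacy gate between the stages: "After testing the drug combination on 16 patients in the first stage, the trial will be terminated if 1 or fewer respond". If the trial continues, 25 patients are studied, so stage 2 adds 9.

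Other sections provide oversight without a count. Section 8.5 has adverse events evaluated continuously and says "The PMC, upon review of any agenda item, may approve the study for continuation, require revisions, suspend or close a protocol". Section 8.6 has the investigator and team monitoring continuously. It also mentions a data and safety plan whose stopping criteria follow the rules in this protocol. Section 5.5 lists adverse drug reactions among the reasons for suspension.

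**The concern.** The section promises strict criteria, but the numeric rule covers 16 of 25 patients. The stage-2 look has no threshold and falls when everyone is already enrolled, so the only stated action, halting accrual, is empty at that point.

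The printed limit at n = 16 is 7, so the trial may open stage 2 with 6 DLTs in 16 (37.5%), one event below its limit and nearly twice the 20% maximum. DLTs in patients 17 to 25 then count towards nothing printed. A committee that sees them accumulate has the power to act but no agreed count at which to do so.

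**Working it through.** **Inputs.** From 10.2.3: the 20% rate, the 0.05 probability and b_1 to b_16. From 10.2.1: 16 patients in stage 1, 25 in total, and continuation only with at least 2 complete responses (CRs). Assumptions: true DLT rates of 30, 40 and 50%; CR and DLT independent; each DLT outcome known before the next patient is counted.

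**Method.** Let f_n(k) be the probability of k DLTs in n patients without having crossed. Then f_n(k) = (1 − p)·f_{n−1}(k) + p·f_{n−1}(k − 1). The probability of halting at n is the sum of f_n(k) over k ≥ b_n; those states are then removed. The efficacy gate multiplies f_16 by G = P(at least 2 CRs in 16).

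**Reproducing the plan.**
- The printed table at p = 0.20 gives total halting probability 0.0496, matching 0.05. Every printed b_n is the smallest count whose binomial tail at 20% is at most 0.0267; the level is set by P(X ≥ 7 | n = 16) = 0.0267.
- At CR 10%, G = 1 − 0.9^16 − 16(0.1)(0.9^15) = 0.485. Expected sample size is 16 + 9 × 0.4853 = 20.37, as printed in 10.2.1. At CR 30%, G = 0.974.

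**The gap as printed.**

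| True DLT rate | 30% | 40% | 50% |
|---|---|---|---|
| Stage 1 ends unhalted at exactly 6/16 | 0.128 | 0.154 | 0.095 |
| Same, and stage 2 opens, CR 10% (× 0.485) | 0.062 | 0.075 | 0.046 |
| No halt and ≥10 of 25, stage 2 always opens | 0.060 | 0.131 | 0.110 |
| No halt and ≥10 of 25, CR 30% | 0.058 | 0.128 | 0.107 |
| No halt and ≥10 of 25, CR 10% | 0.029 | 0.064 | 0.053 |

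**Continuing the same rule.** At pointwise level 0.0267 the next limits are 8 for n = 17–19, 9 for n = 20–22 and 10 for n = 23–25. Their tails at 20% run from 0.009 (n = 23) to 0.023 (n = 19). One event fewer would exceed 0.0267 at every n from 17 to 25; the closest is 0.0273 at n = 23.

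| P(halt) at true rate | 20% | 30% | 40% | 50% |
|---|---|---|---|---|
| Printed (any CR rate) | 0.050 | 0.228 | 0.529 | 0.805 |
| Extended, stage 2 always opens | 0.061 | 0.309 | 0.682 | 0.923 |
| Extended, CR 30% | 0.061 | 0.307 | 0.678 | 0.920 |
| Extended, CR 10% | 0.055 | 0.267 | 0.603 | 0.862 |
| Recalculated for N = 25 at 0.05, stage 2 always opens | 0.050 | 0.276 | 0.652 | 0.912 |

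Expected patients treated at 30/40/50% fall from 21.50/16.74/11.70 to 21.19/16.15/11.20 if stage 2 always opens, and from 17.92/14.56/10.79 to 17.77/14.27/10.55 at CR 10%.

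**Recalculating the whole table for N = 25** raises b_9 from 5 to 6, b_12 from 6 to 7 and b_16 from 7 to 8. Halting by patient 16 falls from 0.228/0.529/0.805 to 0.179/0.447/0.734. Expected patients become 21.76/17.00/11.91, which is 0.2–0.3 more than under the printed rule.

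**The case against.** The text plainly confines continuous monitoring to stage 1, so this is a choice, and the table delivers its stated 0.05. That is right: there is no calibration error here.

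The 20% sentence follows directly after the 25-patient look and might be read as its standard. But the text ties no count or action to 20% at n = 25; the figure calibrates the boundary.

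Stage 2 is not unmonitored. Sections 5.5, 8.5 and 8.6 allow suspension or closure at any time, and the data and safety plan is not among the documents. This limits the point to a missing numeric rule. Section 8.6 sends that plan back to this protocol's rules, and none is printed past n = 16, though further detail in the plan cannot be excluded.

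The gain is modest and the model favourable. DLT rates of 30–50% are hypothetical. The protocol gives no DLT window, and adverse events are collected "until 90 days after the end of pembrolizumab infusions and 30 days after the last dose of ibrutinib", while "The duration of ibrutinib therapy will be up to 51 weeks". With 25 patients planned over 18–24 months, roughly one every 3–4 weeks, some events will surface after later patients enrol, so the patient savings are best-case figures. Late reporting also cuts the other way: a late seventh DLT among the first 16 could still meet b_16 = 7. A crossing at n = 25 spares no enrolment; by n = 24 the extended rule has halted with probability 0.295/0.657/0.908 at 30/40/50% if stage 2 always opens.

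Finally, the extension exceeds the plan's 0.05, whereas recalculation holds it. This is a real trade-off, and the cost needs to be stated openly.

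**Conclusion.** The concern holds and should be fixed. As written, stage 2 can open at 6 DLTs in 16, and no printed limit applies to DLTs in patients 17 to 25 (9 of 25, 36%). If DLTs are known at once, no later count triggers a halt. The chance of finishing with 10 or more DLTs in 25 unhalted is 0.06/0.13/0.11 at true rates of 30/40/50% when stage 2 opens always or nearly always (including CR 30%), and about half that at CR 10%. The gap is therefore widest when the combination is active.

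These figures rest on immediate knowledge of DLTs and on independence of CR and DLT. The absence of a printed count does not depend on either assumption.

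**What to change.** Keep b_1 to b_16 as printed and add b_17–b_19 = 8, b_20–b_22 = 9 and b_23–b_25 = 10. Apply the boundary continuously through stage 2, and restate the stopping probability at a 20% rate as about 0.06. Recalculating the table for N = 25 at 0.05 is not recommended, because it loosens stage 1.

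The section must also reconcile its terms: the 20% rate refers to unacceptable toxicity, while the boundary counts dose-limiting toxicities, and these must be the same event. The sponsor should state the period over which an event counts and which patients n includes, since 5.4.2 permits replacement. The printed table already needs both; their clinical content is for the sponsor.

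The cost is nine table columns, one sentence on stage 2 and these clarifications, with no extra patients or tests and no change to the stage-1 limits. Expected patients treated fall by 0.3–0.6 at DLT rates of 30–50% if stage 2 always opens, or about 0.15–0.3 at CR 10%. The downside is false halting at a 20% rate, which rises from 0.050 to at most 0.061 (0.055 at CR 10%).

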10.2.4 EXPLORATORY ANALYSES

Biological samples for each of the 25 patients enrolled in the trial will be collected at 4 time-points. As the correlative experiments are not the primary focus of the study and are more exploratory in nature, no sample size / power calculations were completed. Summary statistics will be used to summarize the quantitative measures (e.g., cytokine levels, expression levels) for the patients at the 4 time-points with two-sample t-test use to determine if quantitative measurements differ between patients that response and patients that do not response at each time point. When assessing changes in quantitative measurements between time-points (e.g., pre and post treatment measurements) paired t-tests will be used. Longitudinal analysis with linear mixed models will also be used to look for statistical differences between the responders and non-responders using quantitative measurements at all 4 time-points. Correlation between quantitative measurements will be assessed with Spearman correlation.

11 SOURCE DOCUMENTS AND ACCESS TO SOURCE DATA/DOCUMENTS

The PI and other appropriate study staff are responsible for maintaining appropriate medical and research records for this trial, in compliance with ICH E6 and regulatory and institutional requirements for the protection of confidentiality of participants. Representatives of Merck, Janssen, and federal regulatory agencies may examine records for the purpose of quality assurance reviews, evaluation of the study safety, progress of the trial, and data validity.

Source documentation in both electronic and paper form shall be retained for at least two years after the final closure of the trial. These include hospital records, clinical research subject charts (with paper AE logs), research laboratory notes, electronic CRFs, and pharmacy dispensing records.

12 QUALITY ASSURANCE AND QUALITY CONTROL

Quality control procedures will be implemented beginning with the OnCore data entry system and data QC checks that will be run on the database will be generated. Any missing data or data anomalies will be communicated to the staff for clarification/resolution.

Following written SOPs, the Moffitt internal monitors will verify that the clinical trial is conducted and data are generated, documented (recorded), and reported in compliance with the protocol, GCP, and the applicable regulatory requirements (e.g., good laboratory practices (GLP), good manufacturing practices (GMP)).

The investigational site will provide direct access to source data/documents, and reports for the purpose of monitoring and auditing, and inspection by local and regulatory authorities.

All staff will be trained by the PI through a site initiation presentation, power point training for training on the initial protocol for those staff unable to attend the initiation presentation, and ongoing self-study as protocol amendments are approved. Training will be documented on a signature log that will be filed in the electronic regulatory binder.

13 ETHICS/PROTECTION OF HUMAN SUBJECTS

13.1 ETHICAL STANDARD

The investigator will ensure that this study is conducted in full conformity with Regulations for the Protection of Human Subjects of Research codified in 45 CFR Part 46, 21 CFR Part 50, 21 CFR Part 56, and/or the ICH E6.

13.2 INSTITUTIONAL REVIEW BOARD

The protocol, informed consent form(s), recruitment materials, and all participant materials will be submitted to the IRB for review and approval. Approval of both the protocol and the consent form must be obtained before any participant is enrolled. Any amendment to the protocol will require review and approval by the IRB before the changes are implemented to the study. All changes to the consent form will be IRB approved; a determination will be made regarding whether previously consented participants need to be re-consented.

13.3 INFORMED CONSENT PROCESS

13.3.1 CONSENT/ASSENT AND OTHER INFORMATIONAL DOCUMENTS PROVIDED TO PARTICIPANTS

Consent forms describing in detail the study agent, study procedures, and risks will be given to the participant and written documentation of informed consent will be required prior to starting intervention/administering study product.

Other documents to be submitted for review:

- Oral study drug Patient Compliance Diary

13.3.2 CONSENT PROCEDURES AND DOCUMENTATION

Informed consent is a process that is initiated prior to the individual's agreeing to participate in the study and continues throughout the individual's study participation. Extensive discussion of risks and possible benefits of participation will be provided to the participants and their families. Consent forms will be IRB-approved and the participant will be asked to read and review the document. The investigator will explain the research study to the participant and answer any questions that may arise. All participants will receive a verbal explanation in terms suited to their comprehension of the purposes, procedures, and potential risks of the study and of their rights as research participants. Participants will have the opportunity to carefully review the written consent form and ask questions prior to signing.

The participants should have the opportunity to discuss the study with their surrogates or think about it prior to agreeing to participate. The participant will sign the informed consent document prior to any procedures being done specifically for the study. The participants may withdraw consent at any time throughout the course of the trial. A copy of the informed consent document will be given to the participants for their records. The rights and welfare of the participants will be protected by emphasizing to them that the quality of their medical care will not be adversely affected if they decline to participate in this study.

13.4 PARTICIPANT AND DATA CONFIDENTIALITY

Participant confidentiality is strictly held in trust by the participating investigators, their staff, and the

sponsor and their agents. This confidentiality is extended to cover testing of biological samples and genetic tests in addition to the clinical information relating to participants. Therefore, the study protocol, documentation, data, and all other information generated will be held in strict confidence. No information concerning the study or the data will be released to any unauthorized third party without prior written approval of the sponsor.

The Moffitt study monitor, other authorized representatives of Moffitt, representatives of the IRB or pharmaceutical companies supplying study products may inspect all documents and records required to be maintained by the investigator, including but not limited to, medical records (office, clinic, or hospital) and pharmacy records for the participants in this study. The clinical study site will permit access to such records.

The study participant's contact information will be securely stored at each clinical site for internal use during the study. At the end of the study, all records will continue to be kept in a secure location for as long a period as dictated by local IRB and Institutional regulations.

Study participant research data, which is for purposes of statistical analysis and scientific reporting, will be transmitted to and stored at Moffitt. This will not include the participants' contact or identifying information. Rather, individual participants and their research data will be identified by a unique study identification number. The study data entry and study management systems used by clinical sites and by Moffitt research staff will be secured and password protected. At the end of the study, all study databases will be de-identified and archived at the Moffitt.

13.5 FUTURE USE OF STORED SPECIMENS

Data collected for this study will be analyzed and stored at Moffitt Cancer Center. After the study is completed, the de-identified, archived data will be stored at Moffitt Cancer Center, under the supervision of [name], for use by other researchers including those outside of the study. Software tracking programs include FileMaker Pro and Excel.

With the participant's approval and as approved by local IRBs, de-identified biological samples will be stored at [name] lab at Moffitt Cancer Center. These samples could be used for research into the causes of CLL, its complications, and other conditions for which individuals with CLL are at increased risk, and to improve treatment. After completion of the study, samples to be stored will be identified by using only the subject initials and date of collection.

During the conduct of the study, an individual participant can choose to withdraw consent to have biological specimens stored for future research. However, withdrawal of consent with regard to biosample storage will not be possible after the study is completed.

When the study is completed, access to study data and/or samples will be provided through [name] or her successor.

14 DATA HANDLING AND RECORD KEEPING

14.1 DATA COLLECTION AND MANAGEMENT RESPONSIBILITIES

Data collection is the responsibility of the clinical trial staff at the site under the supervision of the site PI. The PI is responsible for ensuring the accuracy, completeness, legibility, and timeliness of the data reported.

All source documents should be completed in a neat, legible manner to ensure accurate interpretation of data. Black ink is required to ensure clarity of reproduced copies. When making changes or corrections, cross out the original entry with a single line, and initial and date the change. All paper source documents will be scanned into the electronic medical record of each subject for storage. DO NOT ERASE, OVERWRITE, OR USE CORRECTION FLUID OR TAPE ON THE ORIGINAL.

Copies of the electronic CRF (eCRF) will be provided for use as source documents and maintained for recording data for each participant enrolled in the study. Data reported in the eCRF derived from source documents should be consistent with the source documents or the discrepancies should be explained and captured in a progress note and maintained in the participant's official electronic study record.

Clinical data (including AEs, concomitant medications, and expected adverse reactions data) and clinical laboratory data will be entered into OnCore, a 21 CFR Part 11-compliant data capture system provided by Moffitt. The data system includes password protection and internal quality checks, such as automatic range checks, to identify data that appear inconsistent, incomplete, or inaccurate. Clinical data will be entered directly from the source documents.

